#### **9.4.8.2 Therapeutic Glucocorticoid Treatment of Elevated Hepatic Transaminases**

Therapeutic oral corticosteroids (prednisone or converted equivalent) should be initiated when either of the following occurs post-BMN 270 infusion in any subject and after consultation with the Medical Monitor:

- ALT  $\geq$  1.5x ULN or ALT  $>$  ULN &  $>$  2x baseline value in 2 consecutive assessments within 72 hours and alternative etiologies have been ruled out, or ALT  $\geq$  3x ULN in 2 consecutive assessments within 48 hours (refer to [Table 9.7.8.3.2](#))
  - Whenever possible, a confirmatory lab draw for ALT should be performed, along with FVIII activity, prior to initiating oral corticosteroids.

- Corticosteroids may be delayed if elevations in ALT are clearly not related to BMN 270 (eg, elevated in ALT with concurrent increase in CPK due to intensive exercise)

The prescribed regimen for therapeutic oral corticosteroids is detailed in [Table 9.1.6](#).

Changes to the corticosteroid regimen should be made as follows:

**Table 9.4.8.2.1: Adjustments to Corticosteroid Regimen**

Tapering Corticosteroid Dose	Subject has been receiving oral corticosteroids <3 weeks	Corticosteroids may be discontinued if: 
 
• ALT < 1.5x ULN or ALT ≤ ULN & ≤ 2x baseline value; and
 
• FVIII levels > 20 IU/dL and within 10% of the pre-decline FVIII levels; and
 
• There is no concern for adrenal insufficiency post-withdrawal
 

	Subject has been receiving oral corticosteroids ≥3 weeks	Corticosteroids may be tapered by 10 mg weekly if: 
 
• ALT < 1.5x ULN or ALT ≤ ULN & ≤ 2x baseline value; and
 
• FVIII levels > 20 IU/dL and within 10% of the pre-decline FVIII levels; and
 
• There is no concern for adrenal insufficiency post-withdrawal
 

Increasing Corticosteroid Dose	If ALT level is increasing or FVIII level is decreasing while on oral corticosteroids, any increases in oral corticosteroid dosing should be made only upon consultation with the Medical Monitor	

For any scenarios that are not accounted for in the above table, a discussion should take place between the Investigator and Medical Monitor regarding corticosteroid dose adjustments.

After discontinuation of oral corticosteroids, labs for ALT and FVIII levels will be measured once a week for 4 weeks to ensure stability in values.

Following initiation or completion of therapeutic oral corticosteroids, if ALT elevation  $\geq 1.5x$  ULN or ALT  $\geq$  ULN &  $\geq 2x$  baseline value is reported, corticosteroid management decisions will be based on discussions between the Investigator and Medical Monitor. Modification of the corticosteroid regimen may take into consideration possible confounders for the ALT elevation and impact on FVIII expression.

Management and monitoring of reactions to corticosteroids should be determined by the Investigator's clinical judgment in consultation with the Sponsor's Medical Monitor. This includes the contraindicated use of NSAIDs during corticosteroid treatment and specific monitoring not already covered by the schedule of events. The use of COX-2 inhibitors, while not contraindicated during corticosteroid treatment, should be limited, if possible.

Practical management to prevent complications related to oral corticosteroid therapy may be undertaken at the discretion of the Investigator (eg, evaluation of glucose intolerance,

hyperlipidemia etc.). Hepatitis B status and HCV viral load will be rechecked 6 weeks after the start of oral corticosteroid treatment and then 1 week and 13 weeks after the completion of oral corticosteroid treatment in subjects with a history of hepatitis B or hepatitis C. All adverse events (including any adverse events suspected to be caused by or related to corticosteroid use) should be reported as outlined in Section 10 of the protocol.

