
Subjects who do not respond to BMN 270 treatment (ie, treatment failure, manifesting as either failure to achieve FVIII activity <math>\geq</math> 5 IU/dL by Week 52 or inability to maintain independence from prophylactic FVIII replacement therapy due to joint bleeding episodes, in the judgment of the Investigator) may, at the Investigator's discretion and after discussion with the Medical Monitor or Sponsor-designated Data Monitor, follow an abbreviated visit schedule after Week 52 of the study by attending only the Q12W and End of Year visits during Years 2-5.
 
There will be an ongoing review of individual subject safety by the Medical Monitor, and both safety and efficacy data by the DMC. Therapeutic oral corticosteroids may be initiated when a subject's ALT values are elevated, and subsequent dosage adjustments made, after consultation between the Investigator and the Medical Monitor.
 
Any safety signal may trigger a review of the data and possible additional immunogenicity studies or other diagnostics deemed necessary that include an assessment of cellular immune responses using collected peripheral blood mononuclear cells (PBMCs).
		

NUMBER OF SUBJECTS PLANNED: Approximately 40 subjects may enroll into the study.
		

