**Table 9.1.6: Schedule of Events – Therapeutic Corticosteroids for ALT Elevations**

	Steroid Treatment Period b								Post-Steroid Period c				
	Week 1	Week 2	Week 3	Week 4	Week 5	Week 6	Week 7	Week 8 b	Week 1	Week 2	Week 3	Week 4	Week 13
Therapeutic corticosteroids (dose in mg/day) a	60 mg	60 mg	40 mg	40 mg	40 mg	30 mg	20 mg	10 mg					
FVIII activity testing									X	X	X	X	
Liver tests									X	X	X	X	
Hepatitis B testing d						X			X				X
HCV Viral Load d						X			X				X

a Therapeutic oral corticosteroids may be initiated according to the parameters set out in Section 9.4.8.2.

b Following initiation or completion of steroid regimen, if a recurrence of ALT values  $\geq 1.5 \times$  ULN or  $>$  ULN and  $> 2x$  baseline value is reported, steroid management decisions will be based on discussions between the Investigator and Medical Monitor. Modification of the steroid regimen may take into consideration possible confounders for the ALT elevation, relationship between increases in ALT and FVIII activity, ALT/FVIII levels post steroid initiation, and adverse events related to steroid dosing. Guidance for tapering oral corticosteroid dosing can be found in Section 9.4.8.2.

c After discontinuation of oral corticosteroids, weekly labs for ALT and FVIII levels will be measured once a week for 4 weeks to ensure stability in values. If these assessments are already being done as part of normal study follow-up, they do not need to be duplicated.

d Should only be performed in subjects with a history of hepatitis B or hepatitis C prior to study entry.

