**Table 9.7.8.3.2: Evaluation of ALT Elevations**

ALT Level	Work-Up
Above ULN and <1.5x ULN	
 
Continue to monitor LTs and FVIII per protocol (repeat within 7 days if next protocol scheduled visit is >7 days from the time of the reported ALT elevation)
 
Consider evaluation to rule out alternative etiology (eg, concomitant medications, viral or autoimmune hepatitis, alcohol use, recreational drug use, special diets, strenuous exercise, prior and/or concurrent illnesses, exposure to environmental and/or industrial chemicals, etc.) (refer to Table 9.7.8.3.3)
 
If ALT is > ULN & > 2x baseline in 2 consecutive assessments within 72 hours and alternative etiologies have been ruled out, start oral corticosteroids upon consultation with the Medical Monitor (refer to Section 9.4.8.2).
 

1.5 - <3x ULN	
 
Repeat LTs and FVIII within 72 hours
 
Continue to monitor LTs weekly until ALT is stable or improving
 
Evaluate and rule out alternative etiologies (as above)
 
Consult with Medical Monitor
 
If ALT is <math>\geq</math> 1.5x ULN in 2 consecutive assessments within 72 hours and alternative etiologies have been ruled out, start oral corticosteroids (refer to Section 9.4.8.2)
 

$\geq$ 3x ULN	
 
Consult with Medical Monitor
 
Evaluate and rule out alternative etiologies (as above)
 
Repeat LTs and FVIII within 48 hours, and continue with monitoring of LTs at least twice weekly for as long as the subject's ALT remains <math>\geq</math> 3x ULN
 
If <math>\geq</math>3x ULN in 2 consecutive assessments within 48 hours, start oral corticosteroids (refer to Section 9.4.8.2)
 
Obtain other possibly relevant laboratory evaluations (albumin, PT/INR, CRP, etc.)
 
Obtain complete blood count with differential to assess for eosinophilia
 
Obtain PBMC to evaluate potential immune response (prior to starting oral corticosteroids)
 
If no improvement in 14 days, consider gastroenterology and/or hepatology consult, abdominal workup, imaging (including MRI or ultrasound), and/or liver biopsy as appropriate
 

When ruling out alternative viral or autoimmune hepatitis as part of the elevated ALT workup, the following tests should be performed:

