14.2 Clinical Laboratory Tests

Clinical laboratory tests include blood chemistry, hematology, urine tests, and coagulation. A supportive listing of abnormal test values with CTCAE v4.03 grade 3 or greater will be produced.

Liver tests by central labs will be assessed on a regular basis, as detailed in the protocol. Summaries of ALT elevations including baseline ALT, time from infusion to ALT > ULN, ALT ≥ 3x ULN, ALT ≥ 5x ULN, ALT ≥ 1.5x ULN or (> ULN & > 2x baseline value), peak ALT level, duration of ALT elevation, corticosteroid treatments for ALT elevations including type, dose, time to initiation of treatment, and duration of treatment will be

provided. Correlation of ALT elevation to FVIII levels, as well correlation of steroid treatment to ALT elevation and FVIII levels will be presented in a listing. Local ALT assessments will be analyzed similarly as the central ALT assessments, if needed. Similar analyses will be applied to other liver tests including aspartate transaminase (AST), gamma-glutamyl transferase (GGT), lactate dehydrogenase (LDH), bilirubin, alkaline phosphatase (ALP), if needed.

In addition, incidences of potential drug-induced liver injury (DILI) that include an elevated ALT or AST in combination with either an elevated bilirubin or clinical jaundice, as defined by Hy's law, will be provided in a data listing.

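### The ALT condition for stopping or tapering corticosteroids reduces to ALT < 1.5x ULN, so it is also met in the lower band that starts them (minor wording correction)

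*Protocol*

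**What the plan says.** **Start rule.** Protocol 9.4.8.2 calls for oral corticosteroids at ALT ≥ 1.5x ULN, or at ALT above ULN and above "2x baseline value in 2 consecutive assessments within 72 hours and alternative etiologies have been ruled out", after Medical Monitor consultation. ALT ≥ 3x ULN confirmed within 48 hours is a further trigger. Table 9.7.8.3.2 puts the baseline-relative trigger in its own row, for ALT above ULN but below 1.5x ULN. The action there, once the elevation is confirmed, is: "alternative etiologies have been ruled out, start oral corticosteroids upon consultation with the Medical Monitor". SAP 14.2 groups the two ALT thresholds the same way, with an explicit parenthesis: "ALT ≥ 1.5x ULN or (> ULN & > 2x baseline value".

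**Stop/taper rule.** Table 9.4.8.2.1 has one row for subjects on steroids for less than 3 weeks (may discontinue) and one for 3 weeks or more (may taper by 10 mg weekly). Both carry the same ALT line: ALT below "1.5x ULN or ALT ≤ ULN" and at or below twice baseline. Both also require FVIII above 20 IU/dL, FVIII within 10% of the pre-decline level, and no adrenal concern.

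**Surrounding text.** Below the table, if ALT is ≥ 1.5x ULN, or at or above both ULN and twice baseline, after steroids have been started or completed, "corticosteroid management decisions will be based on discussions between the Investigator and Medical Monitor". Footnote b of Table 9.1.6 says much the same for recurrence: "steroid management decisions will be based on discussions between the Investigator and Medical Monitor". The Synopsis and Section 9.1 have "subsequent dosage adjustments made, after consultation between the Investigator and the Medical Monitor".

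**The concern.** The start rule has a baseline-relative limb so that a clear rise is treated even when ALT stays below 1.5x ULN. The taper line appears meant to mirror it. Each inequality has been reversed, but the 'or' and the '&' have been left in place, whereas negating such a rule requires swapping them. That account of the origin is inference; the effect does not depend on it.

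As written, the baseline-relative limb of the taper line does nothing. A subject whose ALT is still at a level that would start steroids can satisfy the ALT condition for stopping them. At that same ALT, the text below the table calls for a decision by discussion, so the table and the text do not line up. This is a stated safety rule for managing an event of special interest (Section 10.2.1), so the threshold should say what is meant.

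**Working it through.** No sample size, power or alpha figure is involved; the check is of logic. Write x for ALT and b for baseline ALT, both in multiples of ULN.

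**Rules**

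- ALT part of the start rule (9.4.8.2, Table 9.7.8.3.2): S = (x ≥ 1.5) or (x > 1 and x > 2b).
- Taper line as written (Table 9.4.8.2.1, both rows): T = (x < 1.5) or (x ≤ 1 and x ≤ 2b).
- Baseline range: b up to 1.25, the eligibility cap in exclusion criterion 3 (9.3.2).

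**Step 1: reduce T.** If x ≤ 1 then x < 1.5, so the second limb is contained in the first and T = (x < 1.5).

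**Step 2: overlap with S.** S and T both hold when max(1, 2b) < x < 1.5. This needs 2b < 1.5, that is b < 0.75. The width is 1.5 − max(1, 2b):

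| Baseline (x ULN) | Band (x ULN) | Width (x ULN) |
|---|---|---|
| ≤ 0.5 | 1.0 to 1.5 | 0.5 |
| 0.6 | 1.2 to 1.5 | 0.3 |
| 0.7 | 1.4 to 1.5 | 0.1 |
| ≥ 0.75 | none | 0 |

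ALT ≥ 1.5x ULN is not affected.

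**Step 3: enumeration.** The grid is x = 0.01 to 6.00 and b = 0.05 to 1.25 in steps of 0.01: 600 × 121 = 72,600 pairs. T differs from (x < 1.5) in 0 pairs. S and T both hold in 2,830 pairs, all with x from 1.01 to 1.49 and b ≤ 0.74. By hand: 46 baselines (0.05 to 0.50) × 49 ALT values = 2,254. Baselines 0.51 to 0.74 add 47 + 45 + ... + 1 = 576. The sum is 2,830. These counts test the logic and do not measure patient risk.

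**Step 4: other readings**

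- *Limbs read 'respectively' against the trigger that started treatment.* The text does not say this. For subjects started on the lower trigger the line becomes x ≤ 1 and x ≤ 2b. That removes the overlap, but neither rule then holds in 5,169 pairs, of which 2,070 have a normal ALT (x ≤ 1). At baseline 0.3x ULN, for example, an ALT of 0.61 to 1.00x ULN fails the line. For subjects started at ≥ 1.5x ULN, the 2,830-pair overlap remains.
- *Grouped as (x < 1.5 or x ≤ 1) and x ≤ 2b.* The overlap is 0, but x ≤ 1 is still redundant and the same 2,070 normal-ALT pairs fail. The grouping also conflicts with Table 9.7.8.3.2 and SAP 14.2.

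**Step 5: replacement.** N = (x < 1.5) and (x ≤ 1 or x ≤ 2b). S and N both hold in 0 pairs, and neither holds in 0 pairs.

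**Illustration in U/L.** The documents give no ULN, so these values are assumptions.

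| Assumed ULN | Baseline 20 | Other baselines |
|---|---|---|
| 35 | 40 to 52.5 | 28: none |
| 40 | 40 to 60 | 24: 48 to 60; 28: 56 to 60; 30: none |
| 55 | 55 to 82.5 | 30: 60 to 82.5 |

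**The case against.** The strongest reply is that existing text already covers the whole band. All 2,830 overlapping pairs meet the criterion of the discussion clause below the table, and the Synopsis and Section 9.1 put dosage adjustments after consultation. A subject in the band is therefore discussed and may be tapered both before and after the correction. Section 10.2.1 also requires these ALT levels to be reported to the Sponsor within 24 hours, whatever happens to the steroids. After stopping, "labs for ALT and FVIII levels will be measured once a week for 4 weeks to ensure stability in values".

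It can also be said that start and taper rules apply to subjects in different states. Starting needs confirmation and exclusion of other causes; tapering concerns a treated subject whose FVIII has recovered. A plain taper threshold of 1.5x ULN would be defensible, and nothing requires it to be the exact complement of the start threshold.

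Most of this stands, and it is why the point is minor. It does not rescue the line. If a plain 1.5x ULN threshold was intended, the second limb should not be there; if a baseline-relative limit was intended, it is not in force. The safeguards limit the consequence of the wrong threshold without correcting it. A normal ALT that fails the line under the other readings would not bar tapering, because unlisted scenarios go to discussion, but a normal ALT should not need that route.

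**Conclusion.** The concern holds, as a minor point. The ALT line in both taper rows is equivalent to ALT < 1.5x ULN, and it overlaps the lower steroid-start band for subjects with baseline ALT below 0.75x ULN, over at most 0.5x ULN. This follows from the wording alone; only the U/L examples rest on an assumed ULN. Neither alternative reading repairs the line.

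Practical reach is small. The action is permissive, the FVIII and adrenal conditions must also hold, and SAP Section 1 records that one subject was enrolled and enrollment has been terminated. No effect on steroid dose specific to the band, on any endpoint, or on power or error rates is claimed.

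**What to change.** In both taper rows of Table 9.4.8.2.1, replace the ALT line with:

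**ALT < 1.5x ULN and (ALT ≤ ULN or ALT ≤ 2x baseline value)**

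Add one sentence: when ALT is above ULN and above twice baseline but below 1.5x ULN, the Investigator and Medical Monitor decide together whether to taper or stop.

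The new line is the complement of the ALT thresholds in the start rule. It is not the complement of the whole start rule, which also needs confirmation, excluded etiologies and consultation.

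The cost is one line in two rows plus one sentence, by amendment or clarification letter. The downside is possibly somewhat longer steroid exposure for subjects in the band, including those who have fallen into it from ≥ 1.5x ULN; the added sentence means they are not barred from tapering.

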#### **9.4.8.3 Monitoring of HIV-Positive Subjects**

HIV-positive subjects who have previously enrolled in 270-302 should continue anti-retroviral therapy (ART) as prescribed and follow routine monitoring of CD4 count and viral load ([US Dept Health Human Services, 2014](#)). No alterations in the monitoring are indicated for enrolled immunocompetent HIV-positive subjects who receive corticosteroids as part of their enrollment in 270-302.

#### **9.4.9 Treatment Compliance**

Study drug will be administered to subjects at the study site and/or the dosing facility by a qualified health care professional. The quantity dispensed, returned, used, lost, etc. must be recorded on a dispensing log. Sites will be instructed to return or destroy all used and unused study drug containers.

### **9.5 Investigational Product Accountability**

The Investigator or designee is responsible for maintaining accurate records (including dates and quantities) of IP(s) received and IP lost or accidentally or deliberately destroyed. The Investigator or designee must retain all unused or expired study supplies until the study monitor (on-site CRA) has confirmed the accountability data, if allowed by local SOPs.

#### **9.5.1 Return and Disposition of Clinical Supplies**

Unused study drug must be kept in a secure location for accountability and reconciliation by the study monitor. The Investigator or designee must provide an explanation for any destroyed or missing study drug or study materials (or must be referenced in their institution SOPs).

Unused study drug may be destroyed on site, per the site's standard operating procedures, but only after BioMarin has granted approval for drug destruction. The monitor must account for all study drug in a formal reconciliation process prior to study drug destruction. All study drug destroyed on site must be documented. Documentation must be provided to BioMarin or designee and retained in the Investigator study files. If a site is unable to destroy study drug appropriately, the site can return unused study drug to BioMarin upon request. The return of

---

study drug or study drug materials must be accounted for on a Study Drug Return Form provided by BioMarin.

All study drug and related materials should be stored, inventoried, reconciled, and destroyed or returned according to applicable state and federal regulations and study procedures. For additional information, please refer to the Pharmacy Manual.

## **9.6 Dietary or Other Protocol Restrictions**

There are no dietary or other protocol restrictions for this study. Alcohol should be avoided for the first 52 weeks of the study, and particularly within 48 hours prior to lab work.

Subjects should be advised to abstain from any blood or sperm donation after BMN 270 infusion, until there is no further evidence of vector shedding from PCR analysis of samples.

## **9.7 Safety and Efficacy Variables**

### **9.7.1 Safety and Efficacy Measurements Assessed**

The Schedule of Events ([Table 9.1.1](#) through [Table 9.1.5](#)) describes the timing of required evaluations.

### **9.7.2 Primary Efficacy Variables**

#### **9.7.2.1 FVIII Activity**

The primary efficacy variable is change of the hFVIII activity, as measured by chromogenic substrate assay, during Weeks 49-52 post-BMN 270 infusion from baseline. Each subject's hFVIII activity during Weeks 49-52 is defined as the median of the values obtained during this 4-week window. Values for FVIII activity will be excluded if obtained within 72 hours since the last infusion of exogenous FVIII protein concentrates.

If a subject has used FVIII within 72 hours of a measurement day, all efforts should be made to obtain FVIII activity measurements when a 72-hour interval without FVIII use is achieved; The 72-hour wash-out period is only intended for subjects who have achieved  $FVIII \geq 5$  IU/dL at 16 weeks after BMN 270 infusion and who have not resumed FVIII replacement therapy.

In the event of an FVIII activity level decline during the study:

- If FVIII activity has declined at least 20% from the peak but less than 35% and has declined for at least 2 consecutive assessments, FVIII activity and LTs should be repeated every 7 days until FVIII activity is stable or increasing

- If FVIII activity has declined >35% from the peak and has declined for at least 2 consecutive assessments, FVIII activity and LTs should be repeated every 72 hours until FVIII activity is stable or increasing

Note that fluctuations in FVIII activity are common, and if no clear trend indicating a decline in FVIII activity is observed, then this additional testing may be deferred (upon consultation between the Investigator and the Medical Monitor) until either a more clear trend of decline has been demonstrated or until the FVIII activity levels stabilize or increase.

Subjects who do not respond to BMN 270 treatment [REDACTED]

[REDACTED] may, at the Investigator's discretion and after discussion with the Medical Monitor or Sponsor-designated Data Monitor, follow an abbreviated visit schedule after Week 52 of the study by attending only the Q12W and End of Year visits during Years 2-5.

Details on collecting FVIII activity samples are included in the Laboratory Manual.

### **9.7.3 Secondary Efficacy Variables**

#### **9.7.3.1 Factor VIII Replacement Therapy/Bleeding Episodes**

Secondary efficacy variables are:

- Change of the annualized utilization (IU/kg) of exogenous FVIII replacement therapy during Week 5 to Week 52 post BMN 270 infusion from the baseline utilization of exogenous FVIII replacement therapy.
- Change in the annualized number of bleeding episodes requiring exogenous FVIII replacement treatment during Week 5 to Week 52 of the study post BMN 270 infusion from the baseline ABR.

Subjects must have high quality documented historical data available concerning previous bleeding episodes and exogenous FVIII usage over the previous 12 months in order to be eligible to enroll in the study. During the study, subjects will be asked at each study visit to report the use of factor replacement therapy and the number of bleeding episodes since the previous visit. This information will be captured on the subject's diary or other subject records.

Subjects are strongly encouraged to immediately consult Investigator for guidance regarding exogenous FVIII administration for suspected bleeds or bleeding episodes within the first 30 days post BMN 270 infusion.

In subjects who experience recurrent bleeding episodes, the Investigator and Medical Monitor will discuss whether to resume prior FVIII prophylaxis.

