### **9.3.3 Removal of Subjects from Treatment or Assessment**

Subjects may withdraw their consent to participate in the study at any time without prejudice. The Investigator must withdraw from the study any subject who requests to be withdrawn. Such subjects will always be asked about the reason(s) for withdrawal. The Investigator will discuss with the subject appropriate procedures for withdrawal from the study. The Investigator should ask the subject's consent to perform the procedures listed under the early termination visit. Should a subject withdraw from the study, all efforts will be made to complete and report the observations as thoroughly as possible up to the date of the withdrawal.

A subject's participation in the study may be discontinued at any time at the discretion of BioMarin or of the Investigator and in accordance with his/her clinical judgment. When possible, the tests and evaluations listed for the termination visit should be carried out and every effort will be made to gather follow-up safety data if possible.

BioMarin must be notified of all subject withdrawals as soon as possible. BioMarin also reserves the right to discontinue the study at any time for either clinical or administrative reasons and to discontinue participation by an individual Investigator or site for poor enrollment or noncompliance.

Reasons for which the Investigator or BioMarin may withdraw a subject from the study include, but are not limited to, the following:

- Subject requires medication or medical procedure prohibited by the protocol
- Subject does not adhere to study requirements specified in the protocol
- Subject was erroneously enrolled into the study or does not meet entry criteria and not yet been dosed with BMN 270; subjects who do not meet entry criteria but who erroneously receive BMN 270 should remain in the study for safety monitoring
- Subject is lost to follow-up

If a subject fails to return for scheduled visits, a documented effort must be made to determine the reason. If the subject cannot be reached by telephone, a certified letter should be sent to the subject requesting contact with the Investigator. This information should be recorded in the study records.

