#### **9.4.8 Prior and Concomitant Medications**

All prescription and over-the-counter medications (including dietary and herbal supplements) taken by a subject for 30 days before Screening will be recorded on the designated eCRF.

The Investigator may prescribe additional medications, deemed necessary to provide adequate prophylactic or supportive care, during the study, as long as the prescribed medication is not prohibited by the protocol. In the event of an emergency, any needed medications may be prescribed without prior approval, but the Medical Monitor must be notified of the use of any contraindicated medications immediately thereafter. Any concomitant medications added or discontinued during the study should be recorded on the eCRF. Medications should, whenever possible, not be recorded in the electronic database with a frequency of PRN.

The following medications are prohibited starting 30 days before Screening and through the end of the study, and the Sponsor must be notified if a subject receives any of these during the study:

- Any investigational therapy
- Systemic immunosuppressive agents, except for corticosteroids
- Emicizumab
- Fitusiran
- Concizumab
- Efavirenz
- Lamivudine

The following medications should be avoided, starting 30 days prior to and for at least 52 weeks after BMN 270 infusion and minimized throughout the remaining duration of the study.

- Alcohol
- Herbal and natural remedies and dietary supplements
- Medications which may be hepatotoxic

Vaccines should also be avoided during this period, but in particular during the first 26 weeks unless clinically indicated.

The following medications should be avoided during oral corticosteroid therapy:

- Vaccines
- NSAIDs

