### **10.1.1.1 Bleeding and Suspected Bleeding Events**

All bleeding events and suspected bleeding events, regardless of the need for exogenous FVIII therapy as treatment, should be captured in subject diaries and recorded on the designated bleeding eCRF. Bleeding events and suspected bleeding events should not be reported as adverse events, with the following exception:

- All bleeding events and suspected bleeding events which meet one or more of the criteria for being serious (refer to Section 10.2) should be reported as serious adverse events (whether or not they are bleeding events that are normal sequelae of hemophilia, and whether or not they required exogenous FVIII as treatment).

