### **10.2.1 Events of Special Interest (EOSI)**

The following EOSI need to be reported to the Sponsor within 24 hours of site awareness, irrespective of seriousness, severity or causality:

- Elevation of ALT  $\geq 1.5x$  ULN or ALT  $>$  ULN &  $>2x$  baseline value, regardless of whether that elevation triggers an initiation or modification of oral corticosteroid treatment
- Thromboembolic event
- Systemic hypersensitivity, anaphylactic, or anaphylactoid reactions (refer to Appendix 1)
- Development of anti-FVIII inhibitory antibodies (inhibitors)

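### Both secondary endpoints count only exogenous FVIII, so once a subject starts a non-FVIII hemostatic agent, a complication or failure scores as improvement for the rest of Weeks 5-52

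*Protocol*

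**What the plan says.** Protocol 9.7.3.1 gives two secondary endpoints, tested hierarchically under 14.3:

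- FVIII use: "Change of the annualized utilization (IU/kg) of exogenous FVIII replacement therapy during Week 5 to Week 52 post BMN 270 infusion", compared with baseline.
- Bleeding: "Change in the annualized number of bleeding episodes requiring exogenous FVIII replacement treatment during Week 5 to Week 52 of the study", compared with baseline ABR. It is tested for non-inferiority with a margin of 3.5 and then for superiority.

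Entry (9.3.1) requires at least 12 months of FVIII prophylaxis and no inhibitor history.

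The protocol foresees departures from FVIII. Inhibitor development is an event of special interest (10.2.1), and titers above 5 BU call for urgent DMC evaluation (9.3.3.1). For a list that includes emicizumab, fitusiran and concizumab, 9.4.8 states "The following medications are prohibited starting 30 days before Screening and through the end of the study" but adds that "the Sponsor must be notified if a subject receives any of these during the study". Bypassing agents are not on the list. Section 9.3.3 gives as one reason for which a subject may be withdrawn: "Subject requires medication or medical procedure prohibited by the protocol". For recurrent bleeding, "the Investigator and Medical Monitor will discuss whether to resume prior FVIII prophylaxis" (9.7.3.1).

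On data capture, 10.1.1.1 states: "All bleeding events and suspected bleeding events, regardless of the need for exogenous FVIII therapy as treatment, should be captured in subject diaries". Concomitant medications are recorded on the eCRF (9.4.8). SAP 5.5 defines a baseline ABR for treated bleeds and another for all bleeds. The readable text of SAP section 13, on efficacy, is a heading only, so its content cannot be judged.

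**The concern.** Before infusion a subject's hemophilia treatment is FVIII, so his treated bleeds are counted. After infusion, if he starts another hemostatic agent, bleeds treated with it are observed and recorded but fall outside the endpoint definition. His FVIII consumption drops at the same moment. An immune complication, or a failure managed with another agent, then pulls both endpoints toward improvement. The error cannot run the other way. Section 14.3 offers observed-case analyses and optional multiple imputation, but these address missing data. A subject still in follow-up has no missing data, only data that the definition leaves out. At stake are the superiority claim on ABR and the size of both estimated effects.

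**Working it through.** **The plan's own figure.** Protocol 14.7 states at least 95% power for ABR non-inferiority. Its inputs are N = 35, mean ABR 3.5 before and 1 after, negative binomial dispersion 2.2, margin 3.5, and a one-sample t-test at 2-sided 0.05. I take pre and post as independent and the ABRs as annual counts.

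- Variance as mean + 2.2 × mean²: pre 3.5 + 2.2 × 12.25 = 30.45; post 1 + 2.2 = 3.2; SD of change = √33.65 = 5.80.
- Expected change = 1 − 3.5 = −2.5, so the distance to the margin is 3.5 + 2.5 = 6, and 6/5.80 = 1.03 SD.
- Noncentral t power exceeds 99.9%. Reading the dispersion as mean + mean²/2.2 (SD 3.24) gives the same. The stated figure is confirmed.
- Superiority has less room: 2.5/5.80 = 0.43 SD gives 70% power by noncentral t and 80% by simulation of the skewed counts. Under the smaller variance both exceed 99%.

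**What one switch hides.** Weeks 5-52 are 48 weeks. With a switch at Week s, the affected share is f = (52 − s)/48. If all later bleeds are treated with the new agent at a true rate r per year, r × f is lost from that subject's ABR, and r × f/35 from the mean. The documents give neither s nor r; the values below are assumptions.

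| Switch | f | r = 3.5 | r = 10 | r = 20 |
|---|---|---|---|---|
| Week 16 | 36/48 = 0.75 | 2.625/35 = 0.075 | 7.5/35 = 0.21 | 15/35 = 0.43 |
| Week 26 | 26/48 = 0.54 | 0.054 | 0.155 | 0.31 |
| Week 39 | 13/48 = 0.27 | 0.027 | 0.077 | 0.155 |

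For the Week 16 row this is 0.075/3.5 = 2% to 0.43/3.5 = 12% of the margin, or 0.075/2.5 = 3% to 0.43/2.5 = 17% of the planned effect. Four such subjects shift the mean by 0.30 to 1.71.

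**FVIII use.** Suppose a subject uses FVIII at his full baseline rate from Week 5 to Week 16 and none afterwards. His annualized use is 12/48 = 25% of baseline, so he scores as a 75% reduction.

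**Effect on the tests.** I used 50,000 simulated trials of 35 subjects at each null, with the larger variance, switchers' true ABR assumed to be 10, a Week 16 switch and nominal one-sided 2.5%.

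| Switchers | Superiority rejects | Non-inferiority rejects |
|---|---|---|
| 0 | 2.3% | 5.3% |
| 1 | 3.2% | 6.8% |
| 2 | 4.6% | 8.1% |
| 4 | 9.1% | 11.9% |

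The non-inferiority test already exceeds 2.5% with no switcher because the counts are skewed; only the increase belongs to this point.

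**The case against.** A reader might infer that such a subject scores zero bleeds and zero FVIII use over the whole period, the best possible result. The documents do not support that. FVIII use and FVIII-treated bleeds from Week 5 up to the switch still count, so a full zero needs no FVIII at all over 48 weeks.

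A reader might also infer that any treatment failure takes this route. The path described for recurrent bleeding is a discussion of resuming FVIII prophylaxis, which the utilization endpoint registers. FVIII also stays available for acute bleeds (9.4.8.1). A subject without an inhibitor who starts another prophylactic agent but treats breakthrough bleeds with FVIII would have those bleeds counted, although his FVIII use would still fall. The ABR gap is therefore mainly an inhibitor followed by bypassing treatment.

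Notification is not the only consequence of prohibited agents, since withdrawal is possible. A withdrawn subject's later time would be missing data, and scoring it as zero would be an inference from silence. Withdrawal is optional, however, and does not settle how a subject who stays is counted.

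It is tempting to size the effect with the protocol's on-demand range of 20 to 60 bleeds/year. Those are median ABRs for on-demand FVIII therapy in prospective FVIII studies and do not describe subjects with inhibitors or on non-FVIII agents.

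Finally, such cases are not hidden from view. The primary endpoint, FVIII activity, is tested first, and inhibitors are reported and listed as events of special interest. The contents of the supplied interim SAP also refer to a study SAP that is not among the documents. All of this limits the consequence. None of it changes the protocol's endpoint definitions.

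**Conclusion.** The point holds in a limited form. Both secondary endpoints count FVIII alone, the protocol foresees situations in which another agent is used, and no readable rule covers them. From the switch onward the scoring errs only in favour of BMN 270. One subject moves the mean ABR change by about 0.075 to 0.43 per year, given the assumed Week 16 switch, the assumed rates of 3.5 to 20 per year, and later bleeds all treated with the new agent. Under the planned means non-inferiority would survive this easily; the exposure lies mainly in the superiority test and the estimates. Few cases are expected, because the summary for Amendment 4 says that no neutralizing antibodies had been observed in BMN 270 studies. The SAP reports one enrolled subject, terminated enrollment and listings only, so no hypothesis test will be affected. The flaw is in the plan as written.

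**What to change.** In Protocol 9.7.3.1 and 14.3:

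1. Define the ABR endpoint as bleeds requiring any hemostatic treatment: FVIII, a bypassing agent or another hemophilia product.
2. Add an ABR for all recorded bleeds as a supportive analysis, matching the all-bleeds baseline in SAP 5.5.
3. Keep measured FVIII use as the utilization endpoint, flag subjects who start a non-FVIII agent, and report a sensitivity analysis that credits no reduction after the switch. Assigning the baseline rate in the main analysis is a debatable choice of estimand and is not needed here.

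The cost is wording and a derivation rule, since all bleeds and concomitant medications are already recorded. The documents do not show whether the bleeding form names the agent used for each bleed; if it does not, bleeds must be linked to medication records by date. The endpoints may become slightly less favourable. Nothing here implies which agents a subject should receive.
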